Methods / trial design: This trial is a prospective, multicenter, open-label, non-controlled trial in female subjects, age 15 and above who present to the clinic seeking contraception, who are postmenarcheal and premenopausal. Breastfeeding women are allowed to participate in the trial. At V1a (screening), informed consent/assent will be obtained and the screening procedures will be performed. At V1b, after the results of the laboratory tests have confirmed the subject's eligibility, the subject will be provided with the investigational medicinal product (IMP) and an electronic diary and the subject will be instructed in their use. Afterwards, the subjects will attend Visits 2 to 5 at Day 20±2 of the 1 st , 3 rd , 6 th and 9 th cycle and Visit 6 at Day 29+2 of the 13 th cycle. The follow-up (Visit 7) will take place 10-14 days after Visit 6. Once a month, on Day 10 (+ 2 days) of each cycle, the subjects will be contacted by the site staff to collect information on any adverse events which might have occurred. The trial will include women who have never used hormonal contraceptives before consent/assent (naïve users), women who have not used hormonal contraceptives in the past three months before consent/assent or who have used hormonal contraceptives in the past but have a contraceptive-free time of less than three months before consent/assent (previous users) as well as women directly switching from another hormonal method (switchers). Women who have used hormonal contraceptives in the past but have a contraceptive-free time of less than three months before consent/assent are allowed to be included into the trial if they had at least one complete menstrual cycle before enrollment. For naïve users and previous users, the first IMP intake will be on the first day of the next menstrual bleeding after Visit V1b. (If the menstrual bleeding starts in the evening, and the subject prefers to take her pill in the morning, then she may begin the first IMP intake the next day [Day 2 of the menstrual bleeding]). For a switcher, the first IMP intake will be on	

the day following the last active pill of the previous hormonal contraceptive. The subject is free to choose an intake time in the morning or evening that suits her requirements.

Breastfeeding women can start the first IMP any day starting six weeks after delivery.

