1. FLOW CHART AND VISIT SCHEDULE

Table 1: Schedule of Trial Procedures

Visits		V1a (Screening)	V1b (Medication Dispensation)	V2	V3	V4	V5	V6/EDV	V7 (Follow-Up)
Medication cycle	3 to 4 weeks			1	3	6	9 ⁽¹⁵⁾	13 ⁽¹⁾	10 to 14 days after V6⁽²⁾
				Day 20 ± 2 of medication cycle				Day 29 +2	
Informed consent/assent	x								
Demography	x								
Medical and gynecological history ⁽³⁾	x								
Prior medication/contraceptive devices	x								
Concomitant medication/contraceptive devices	x		x	x	x	x	x	x	
Wish of pregnancy ⁽¹³⁾	x	x	x	x	x	x	x	x	
Physical examination	x				x			x	
Vital signs ^(4, 11) , body weight and height ⁽⁷⁾	x	x	x	x	x	x	x	x	
Gynecological examination	x				x			x	
Transvaginal ultrasound	x							x	
Cervical cytology (Pap smear)	x ⁽¹⁹⁾							x ⁽¹⁹⁾	
Routine laboratory parameters ⁽⁵⁾	x		x ⁽¹⁷⁾	x ⁽¹⁰⁾	x	x ⁽¹⁰⁾	x	x	
Pharmacokinetic analysis ⁽¹²⁾			x		x				
Urinalysis ⁽⁶⁾	x				x			x	
Serum pregnancy test	x								
Urine pregnancy test ⁽⁸⁾		x	x	x	x	x	x	x	x
In-/exclusion criteria	x	x							
Dispensing of IMP		x ⁽²⁰⁾	x	x	x	x			
Drug accountability			x ⁽¹⁸⁾	x	x	x	x	x	
IMP acceptability ⁽¹⁶⁾				x				x	
Discuss consecutive contraceptive method						x			
Dispense/collect e-diary		x ⁽¹⁴⁾						x	
Review e-diary ⁽⁹⁾			x	x	x	x	x	x	
Adverse events ⁽⁹⁾	x	x	x	x	x	x	x	x	x

- 1 Assessments are to be performed after completion of cycle 13 and also in case of early discontinuation.
- 2 The post treatment evaluation is to be performed by interviewing the subjects. Inquiries are to be made regarding menstrual cycle, possible return of fertility, and possible use of contraceptive.
- 3 Including check of venous thromboembolism (VTE) risk.

4 Blood pressure and pulse.

5 Laboratory parameters: hematology, biochemistry.

Hematology: hemoglobin, red blood cell count, mean corpuscular volume (MCV) and associated parameters, hematocrit, MCH, white blood cell count, differential white blood cell count including neutrophils, lymphocytes, eosinophils, basophils and monocytes, platelet count.

Biochemistry: sodium, potassium, chloride, creatinine, blood urea nitrogen (BUN), calcium, glucose, total proteins, albumin, total cholesterol (HDL, LDL cholesterol), triglycerides, gamma glutamyl transferase, total and direct bilirubin, alkaline phosphatase (ALP), alanine aminotransferase (ALAT), aspartate aminotransferase (ASAT), creatine phosphokinase (CPK), lactate dehydrogenase (LDH).

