2.3 Overall Trial Design

This trial is a prospective, multicenter, open-label, non-controlled trial in female subjects, age 15 or above who present to the clinic seeking contraception, who are postmenarcheal and premenopausal. Breastfeeding women are allowed to participate in the trial.

At V1a (screening), informed consent/assent will be obtained and the screening procedures will be performed. At V1b, after the results of the laboratory tests have confirmed the subject's eligibility, the subject will be provided with the investigational medicinal product (IMP) and an electronic diary and the subject will be instructed in their use. On anticipated start date of Cycle 1+2 days, the trial staff will call the subject for the confirmation of IMP start date. Afterwards, the subjects will attend Visits 2 to 5 at Day 20±2 of the 1st, 3rd, 6th and 9th cycle and Visit 6 at Day 29±2 of the 13th cycle. The follow-up (Visit 7) will take place 10-14 days after Visit 6. Once a month, on Day 10 (+ 2 days) of each cycle, the subjects will be contacted by the site staff to collect information on any adverse events which might have occurred.

The trial will include women who have never used hormonal contraceptives before consent/assent (naïve users), women who have not used hormonal contraceptives in the past three months before consent/assent or who have used hormonal contraceptives in the past but have a contraceptive-free time of less than three months before consent/assent (previous users) as well as women directly switching from another hormonal method (switchers). Women who have used hormonal contraceptives in the past but have a contraceptive-free time of less than three months before consent/assent are allowed to be included into the trial if they had at least one complete menstrual cycle before enrollment.

For naïve users and previous users, the first IMP intake will be on the first day of the next menstrual bleeding after Visit V1b. (If the menstrual bleeding starts in the evening, and the subject prefers to take her pill in the morning, then she may begin the first IMP intake the next day [Day 2 of the menstrual bleeding]). For a switcher, the first IMP intake will be on the day following the last active pill of the previous hormonal contraceptive. The subject is free to choose an intake time in the morning or evening

that suits her requirements. Breastfeeding women can start the first IMP any day starting six weeks after delivery.

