4.6 Trial Periods

Date of the first IMP intake

The date of the first IMP intake will be defined as the date of the first IMP intake recorded in the treatment diary.

If such date is not available and subject did not return all IMP pills, Visit 1b date will be taken into account.

Date of the last IMP intake

The date of last IMP intake will be defined as the date of the last IMP intake provided in the eCRF “Trial Termination” section.

If such date is incomplete the following will be imputed:

- The date of the last day of the month, if month and year is available but the day is missing.

If such date is not available or only year is provided, last date of IMP administration recorded in subject's diary will be taken into account. If last date of IMP administration recorded in subject's diary is not available and subject did not return all IMP pills, the subject's last visit date will be taken into account.

Treatment period

The treatment period is defined as the period from the first IMP intake up to the last IMP intake.

Baseline value

Baseline value for a variable will be defined as Visit 1a value.

Absolute change

Absolute change from Visit 1a to each visit will be calculated as

$$\text{Absolute change from Baseline at Visit } <X> = \text{Value at Visit } <X> - \text{Baseline Value.}$$

Treatment cycle

Treatment cycles will be defined as 28 days periods starting on the day of the first IMP intake from the blister containing 28 tablets. No more than 13 completed cycles will be used for analysis.

Reference period

The treatment period will be grouped into reference periods as:

- Cycles 2-4
- Cycles 5-7
- Cycles 8-10
- Cycles 11-13

Overall period

- Cycles 2-13

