5.7.1 Bleeding Pattern

The number and rate of subjects with different bleeding and spotting patterns will be presented for each cycle. The Clopper-Pearson 95% CI for vaginal bleeding or spotting rate of subjects will be calculated using the **PROC FREQ** procedure:

```
PROC FREQ DATA=<data set>;
  BY <by variable>;
  TABLES <endpoint variable> / BINOMIAL;
RUN;
```

The following definitions will be applied:

Episode of bleeding/spotting – bleeding/spotting days bounded on either end by two days of no bleeding or spotting. Missing data will be considered as bleeding/spotting day if it is bounded on bleeding/spotting days or one days of no bleeding or spotting.

Days of bleeding/spotting – presence of bleeding/spotting on actual day.

Scheduled bleeding/spotting – any bleeding or spotting that occurs during hormone-free intervals (defined as Days 25-28 ± 1 day). Bleeding/spotting that starts during this period and continues for up to eight consecutive days is considered as scheduled bleeding/spotting.

If scheduled bleeding starts in Cycle X but ends in Cycle (X+1) then bleeding episode will be assigned to Cycle X.

Any bleeding or spotting that occurs during cycle Days [1-8] of the first treatment cycle and lasts up to 8 consecutive bleeding/spotting days will also be considered as scheduled bleeding days.

Unscheduled bleeding/spotting – any bleeding/spotting that occurs outside the time window defined for scheduled bleedings.

Cumulative rate of subjects with different bleeding and spotting patterns for reference periods (summary of cycles 2-4, 5-7, 8-10 and 11-13) will be provided. Cumulative rates only for reference periods will also be presented for number and percent of subjects with prolonged bleeding and spotting > 9 days/ > 14 days and the number of bleeding and spotting episodes.

Number and percent of days per cycle and reference period with bleeding and spotting, scheduled bleeding, unscheduled bleeding, scheduled spotting or unscheduled spotting and duration of scheduled bleeding, scheduled spotting, unscheduled bleeding and unscheduled spotting will be analyzed descriptively.

Cycles without consecutively missing diary entries and with less than five non-consecutive missing diary entries will be used in the bleeding pattern analysis.

Tables

No.	Name	Analysis set	Comments

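### Scheduled bleeding days and scheduled-episode duration are cut short in cycle 13, because the carry-over rule has no next cycle to draw on and the e-diary is collected at Visit 6

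*SAP*

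**What the plan says.** SAP 5.7.1 places scheduled bleeding and spotting in the hormone-free interval, "defined as Days 25-28 ± 1 day". On length it says: "Bleeding/spotting that starts during this period and continues for up to eight consecutive days is considered as scheduled bleeding/spotting". For a bleed that crosses into the next blister it adds: "If scheduled bleeding starts in Cycle X but ends in Cycle (X+1) then bleeding episode will be assigned to Cycle X".

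Observation ends soon after cycle 13. SAP 4.6 defines cycles as 28-day periods and states: "No more than 13 completed cycles will be used for analysis". In the schedule of procedures (SAP section 1), the row "Dispense/collect e-diary" is marked at V1b and at V6/EDV, with no mark at V7. A footnote to the schedule says of that follow-up: "The post treatment evaluation is to be performed by interviewing the subjects".

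The timing of Visit 6 is not consistent. The protocol synopsis has "Visit 6 at Day 29+2 of the 13 th cycle", and SAP section 1 and SAP 4.4 agree with it. SAP 2.3 has "Visit 6 at Day 29±2 of the 13th cycle". These passages must be reconciled.

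Scheduled days and episode duration are tabulated by cycle and by reference period (Tables 15.4.1.6.1, 15.4.2.6.1 and 15.4.3.2.1). The supplied text has no rule for the last observed cycle.

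**The concern.** The carry-over rule works only if there is a following cycle with diary data. A scheduled bleed that starts late in cycle 8 is completed from the cycle 9 diary. One that starts late in cycle 13 stops, for analysis purposes, on the last diary day. Cycle 13 also hands its own early spill-over days back to cycle 12, so it gives days away and cannot recover the ones it loses at its end.

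The error has one direction: the cut-off can lower scheduled days and scheduled duration in cycle 13 but cannot raise them. The results are laid out as a sequence of reference periods ending in 11-13, so a constant bleeding pattern would show a fall in the last period and could be read as improvement with longer use. The trial is non-controlled, so no comparator would reveal that the fall comes from the counting rule.

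**Working it through.** The plan states no figure for this, so there is none to reproduce. The check is a direct enumeration.

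**Inputs from the documents**
- Onset day s: the window with its one-day margin runs from Day 24 to Day 29. Day 29 is already outside the 28-day cycle, so onsets inside cycle 13 are Days 24 to 28.
- Bleed length L: at most 8 days. A bleed can therefore run to Day 24 + 7 = 31 at the earliest onset and Day 28 + 7 = 35 at the latest.
- Last diary day C: 29, 30 or 31 under the Day 29+2 timing.

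**Assumptions, not in the documents**
- Onset is uniform on Days 24 to 28.
- L is constant; a range is shown.
- One scheduled bleed occurs per cycle.
- The diary runs through the day of Visit 6.

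**Step 1. Recorded days in cycle 13 = min(L, C − s + 1).** For L = 5:

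| Onset day | C = 29 | C = 30 | C = 31 |
|---|---|---|---|
| 24 | 5 | 5 | 5 |
| 25 | 5 | 5 | 5 |
| 26 | 4 | 5 | 5 |
| 27 | 3 | 4 | 5 |
| 28 | 2 | 3 | 4 |
| Mean | 3.8 | 4.4 | 4.8 |
| Loss against 5 | 1.2 (24%) | 0.6 (12%) | 0.2 (4%) |

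**Step 2. Other lengths, mean loss in cycle 13.**

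| L | C = 29 | C = 30 | C = 31 |
|---|---|---|---|
| 3 | 0.2 d (7%) | 0 | 0 |
| 4 | 0.6 d (15%) | 0.2 d (5%) | 0 |
| 5 | 1.2 d (24%) | 0.6 d (12%) | 0.2 d (4%) |
| 8 | 4.0 d (50%) | 3.0 d (38%) | 2.0 d (25%) |

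**Step 3. Dilution over a period.** Cycles 11 and 12 are complete, so the period 11-13 mean is (2L + recorded)/3 and its relative loss is one third of the cycle 13 loss. For L = 5 that is 24%/3 = 8%, 12%/3 = 4% and 4%/3 ≈ 1%. For L = 8 it is about 17%, 12.5% and 8%. Over cycles 2-13 the divisor is 12, so L = 5 loses 2%, 1% or about 0.3%.

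**Step 4. Why the loss concentrates in cycle 13.** SAP 2.6 assumes 45% dropout. If that is spread at a constant rate over 13 cycles (assumption), 1 − 0.55^(1/13) ≈ 4.5% of women per cycle stop before the next. Only those who stop at or just after a cycle boundary lose days in the same way. In cycle 13 every woman still on treatment is exposed to the cut-off.

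**Step 5. Closing an episode.** SAP 5.7.1 requires two bleed-free days on either side of an episode. For both to be recorded, bleeding must end by Day 27, 28 or 29 when the diary ends on Day 29, 30 or 31. The supplied text does not say how an unclosed last episode enters the duration table.

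**Step 6. Counting by day of occurrence.** With L = 5 and onset on Days 24 to 28, the days that fall inside Days 1-28 number 5, 4, 3, 2 and 1, mean 3.0, and a mean of 2.0 spill into the next cycle. Cycle 13 would then hold 3.0 of its own days plus 2.0 from cycle 12, which is 5.0, the same as any earlier cycle. The artificial loss of days disappears. Episode duration would still be cut off at the last diary day.

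**The case against.** The best case against is that the effect is small and partly visible. With short bleeds and a diary kept to Day 31 it is zero, and period 11-13 dilutes it to a third. The tables are also by cycle, so a drop confined to cycle 13 could be seen, and some planned tables count women by treatment day. The outputs are descriptive. All of this stands and limits the size. It does not remove the bias: a reader who sees a cycle 13 drop cannot tell truncation from a real change, and the reference-period row hides the source.

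Several stronger readings are tempting but not supported:

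- **Total bleeding days (Table 15.4.1.4.1) also fall.** SAP 5.7.1 defines a bleeding day by its presence on the actual day, and Days 1-28 of cycle 13 are fully inside the diary. That table is affected only if the episode rule is carried into it, which the definition does not suggest.
- **Prolonged bleeding over 9 or 14 days (Table 15.4.3.3.1) is distorted by this rule.** A scheduled bleed lasts at most eight days, so the rule cannot be the cause. What remains is ordinary censoring at the end of observation.
- **Every early discontinuer is affected.** A woman who stops mid-cycle has diary days that can complete the bleed of her last full cycle. Only stops at or just after a boundary matter.
- **Data end at Day 28, or bleeds start on Day 29.** A Day 28 cut would raise the 5-day loss to 40% of cycle 13 (2.0 of 5 days) and about 13% of period 11-13. The limit of 13 completed cycles does not say that diary entries on Days 29-31 are discarded for a bleed already under way. A bleed starting on Day 29 does not start in cycle 13, so the carry-over rule does not cover it.

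The protocol is available only as a synopsis, and the table specifications listed in the SAP appendices are not reproduced. A last-cycle rule could exist there.

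**Conclusion.** The point holds for scheduled bleeding and spotting days and for scheduled-episode duration, in cycle 13 and in reference period 11-13. The direction follows from the text, provided the scheduled-day counts follow the cycle to which the episode is assigned. This is the natural reading, but the SAP does not spell it out.

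The size cannot be fixed from the documents. For 5-day bleeds under the stated assumptions it is modest, about 1% to 8% in period 11-13. It is near zero for 3-day bleeds, and reaches a quarter to a half of cycle 13 for 8-day bleeds. If SAP 2.3 were followed and the diary ended on Day 27, a 5-day bleed would lose 3.0 days (60%) in cycle 13, so the Visit 6 timing has to be reconciled before the loss can be judged.

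The consequence is a possibly misleading tolerability trend. The Pearl Index, and the share of women with any scheduled bleeding apart from Day 29 onsets, are essentially unaffected.

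**What to change.** In SAP 5.7.1:

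1. For scheduled days and scheduled-episode duration, treat a bleed still open on the last diary day as right-censored. Base the by-period trend on per-cycle means that leave out cycle 13 for all women, whether or not a bleed started. Leaving out only cycles with a bleed would keep the zeros and bias the mean downward. Report cycle 13 separately, flagged as truncated. Keep it for the yes/no count of any scheduled bleeding and for total days.
2. Add one version of the scheduled-days tables that counts each bleeding day in the cycle where it occurs.
3. State that total days per cycle are counted by actual day.

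Separately, reconcile the Visit 6 timing between the protocol synopsis, SAP section 1 and SAP 4.4 on one side and SAP 2.3 on the other.

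The cost is a few sentences of SAP text and the reprogramming of a few tables; no new data are needed. Cycle 13 no longer contributes to the scheduled-duration trend. Because the SAP evaluates all tolerability variables over 13 cycles, the exception should be stated openly.

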2.1.2 Secondary Objectives

The secondary objectives of this trial are to demonstrate the safety and tolerability of LF111 and to assess the pharmacokinetics of LF111.

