2.2.4 Tolerability endpoints

The tolerability endpoints are based on vaginal bleeding pattern and include the following variables:

Bleeding:

- Number of subjects with bleeding by treatment day, treatment cycle and reference period (summary of cycles 2-4, 5-7, 8-10, 11-13 and 2-13)
- Number of subjects with unscheduled bleeding days by treatment cycle and reference period
- Number of subjects with scheduled bleeding days by treatment cycle and reference period
- Number of subjects with prolonged bleeding >nine days/ >14 days by reference period
- Number of bleeding episodes during treatment and by reference period
- Number of days with bleeding by cycle and reference period
- Number of days with unscheduled bleeding by cycle and reference period
- Number of days with scheduled bleeding by cycle and reference period
- Mean length of bleeding episodes by cycle and reference period

Spotting:

- Number of subjects with spotting by treatment day, treatment cycle and reference period (summary of cycles 2-4, 5-7, 8-10, 11-13 and 2-13)
- Number of subjects with unscheduled spotting days by treatment cycle and reference period
- Number of subjects with scheduled spotting days by treatment cycle and reference period
- Number of subjects with prolonged spotting >nine days/ >14 days by reference period
- Number of spotting episodes during treatment and by reference period
- Number of days with spotting by cycle and reference period
- Number of days with unscheduled spotting by cycle and reference period
- Number of days with scheduled spotting by cycle and reference period
- Mean length of spotting episodes by cycle and reference period

Only cycles of women with complete and correct diary entries will be taken into account in the analysis.

All tolerability variables will be evaluated over 13 cycles.

Another tolerability endpoint is the IMP acceptability.

Tolerability Endpoints in Addition to the Protocol

In addition, tolerability endpoints that are based on vaginal bleeding pattern and on combined variables (bleeding/spotting) will be evaluated:

- Number of subjects with bleeding/spotting by treatment day, treatment cycle and reference period
- Number of subjects with unscheduled bleeding/spotting days by treatment cycle and reference period
- Number of subjects with scheduled bleeding/spotting days by treatment cycle and reference period
- Number of subjects with no bleeding/spotting days by treatment cycle and reference period

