2.6 Sample Size

At least 920 subjects will be allocated to treatment to have at least 5000 evaluable cycles for the PI calculation in non-breastfeeding women aged ≤ 35 years (at the time of trial enrollment). Additionally, a minimum of 75 subjects aged > 35 years will be allocated to treatment. The calculations are based on empirical values including firstly a rate of 24.8% of subjects using back-up contraception or not having intercourse. Secondly, 45% of subjects are assumed to drop out of the trial. The prime target is to collect at least 5000 evaluable cycles.

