5.7 Tolerability Analysis

The tolerability assessment includes the vaginal bleeding pattern and the IMP acceptability. Analysis of tolerability endpoints will be conducted using the FAS.

All tolerability variables will be evaluated over 13 cycles.

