Table 15.4.1.1.1	Number of Subjects with Bleeding by Treatment Day, Treatment Cycle and Reference Period	Full Analysis	Number and percentage of subjects in respective time point will be presented. Percentage will be based on the number of subjects with respective cycles available. Data of centers 104 and 120 will be excluded.
Table 15.4.1.2.1	Number of Subjects with Unscheduled Bleeding Days by Treatment Cycle and Reference Period	Full Analysis	Number and percentage of subjects in respective time point will be presented. Percentage will be based on the number of subjects with respective cycles available. Data of centers 104 and 120 will be excluded.
Table 15.4.1.3.1	Number of Subjects with Scheduled Bleeding Days by Treatment Cycle and Reference Period	Full Analysis	Number and percentage of subjects in respective time point will be presented. Percentage will be based on the number of subjects with respective cycles available. Data of centers 104 and 120 will be excluded.
Table 15.4.1.4.1	Number of Days with Bleeding by Cycle and Reference Period	Full Analysis	Number of days will be summarized as continuous data. Number of days will be based on the number of subjects with respective cycles available. Data of centers 104 and 120 will be excluded.
Table 15.4.1.5.1	Number of Days with Unscheduled Bleeding by Cycle and Reference Period	Full Analysis	Number of days will be summarized as continuous data. Number of days will be based on the number of subjects with respective cycles available. Data of centers 104 and 120 will be excluded.
Table 15.4.1.6.1	Number of Days with Scheduled Bleeding by Cycle and Reference Period	Full Analysis	Number of days will be summarized as continuous data. Number of days will be based on the number of subjects with respective cycles available. Data of centers 104 and 120 will be excluded.
Table 15.4.2.1.1	Number of Subjects with Spotting by Treatment Day, Treatment Cycle and Reference Period	Full Analysis	Number and percentage of subjects in respective time point will be presented. Percentage is based on subject with respective cycle available. Data of centers 104 and 120 will be excluded.
Table 15.4.2.2.1	Number of Subjects with Unscheduled Spotting Days by Treatment Cycle and Reference Period	Full Analysis	Number and percentage of subjects in respective time point will be presented. Percentage will be based on the number of subjects with respective cycles available. Data of centers 104 and 120 will be excluded.

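### The bleeding tables by cycle and reference period use only women with that cycle available, so selective dropout can look like improvement over 13 cycles, and no planned bleeding table would show it

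*SAP*

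**What the plan says.** Tolerability is part of the secondary objective in SAP 2.1.2: "The secondary objectives of this trial are to demonstrate the safety and tolerability of LF111". The tolerability endpoints are the vaginal bleeding pattern and IMP acceptability, and SAP 2.2.4 adds: "All tolerability variables will be evaluated over 13 cycles".

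SAP 5.7 names the analysis set: "Analysis of tolerability endpoints will be conducted using the FAS". The denominators in the tables of SAP 5.7.1 are narrower. For tables of subjects the rule is "Percentage will be based on the number of subjects with respective cycles available"; for tables of days it is "Number of days will be based on the number of subjects with respective cycles available". A diary rule narrows them again: "Cycles without consecutively missing diary entries and with less than five non-consecutive missing diary entries will be used in the bleeding pattern analysis". Results appear by cycle and for cycles 2-4, 5-7, 8-10, 11-13 and 2-13.

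On dropout, SAP 2.6 says: "Secondly, 45% of subjects are assumed to drop out of the trial". SAP 4.10 leaves missing data to the subsections of Section 5. Within 5.7.1 the only rules concern missing diary days: filling gaps around an episode, and deciding which cycles are usable. Neither deals with women who have left.

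**The concern.** The trial has one arm and follows women for 13 cycles. A row of columns running from cycles 2-4 to cycles 11-13 will naturally be read as the course of bleeding on LF111. What each column reports is bleeding among the women who still contribute at that time. If leaving is related to bleeding, the group changes from column to column and the percentage moves even when every woman's own pattern is constant. There is no control arm to show how much of a trend is selection.

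The SAP uses within-woman comparison elsewhere. IMP acceptability has a shift table from V3 to V6/EDV (5.7.2). Ultrasound, dysmenorrhea, mastodynia and cytology have shift tables from baseline to EDV, V6 and V6/EDV (5.6.5.2 to 5.6.6). The bleeding pattern has no such table and none split by later withdrawal. A reader who saw a decline could not tell whether women bled less or whether women who bled more had gone.

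**Working it through.** **1. The plan's own figure.** The 45% comes from the sample size (SAP 2.6: 920 women, 5000 evaluable cycles, 24.8% without qualifying intercourse, 45% dropout).

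920 × 13 × (1 − 0.248) × (1 − 0.45) = 4947 cycles, 1.1% below 5000.

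The figure reproduces if women who drop out contribute no cycles. The documents therefore give a total for dropout but no timing and no reasons. The steps below assume a constant hazard reaching 45% after 13 cycles.

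**2. How far the columns shrink.** If everyone has the same hazard h, exp(−13h) = 0.55, so h = −ln(0.55)/13 = 0.0460 per cycle. Each cycle in 11-13 lies nine cycles after its partner in 2-4, so the ratio of women remaining is exp(−9h) = 0.55^(9/13) = 0.66. It stays at 0.66-0.67 when the hazard differs between two groups by a ratio of 1 to 3. The diary rule may remove further cycles; that effect is not modelled.

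**3. A two-group model with no change in any woman.** A proportion p of women are in a high-bleeding group at the start. Their dropout hazard is HR times that of the others. Solve for h:

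(1 − p)·exp(−13h) + p·exp(−13h·HR) = 0.55

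The high-bleeding share at cycle c is p·exp(−h·HR·c) / [p·exp(−h·HR·c) + (1 − p)·exp(−h·c)], averaged over cycles 2-4 and over 11-13. Reported percentage = bL + (bH − bL) × share, where bH and bL are the fixed proportions of cycles with bleeding in each group.

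Example with p = 0.5 and HR = 2. Put x = exp(−13h); then x² + x − 1.1 = 0, x = 0.662 and h = 0.0317. Dropout over 13 cycles is 33.8% in the low group and 56.2% in the high group, averaging 45%. The high-bleeding share falls from 0.476 to 0.406. With bH = 0.8 and bL = 0.3 the reported percentage goes from 0.3 + 0.5 × 0.476 = 53.8% to 0.3 + 0.5 × 0.406 = 50.3%, a relative fall of 7%.

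Percentage bleeding, cycles 2-4 to cycles 11-13, with the relative fall:

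| p | HR | 80% / 30% of cycles | 100% / 0% of cycles |
|---|---|---|---|
| 0.5 | 1 | 55.0 to 55.0 (0%) | 50.0 to 50.0 (0%) |
| 0.5 | 1.5 | 54.3 to 52.2 (4%) | 48.6 to 44.4 (9%) |
| 0.5 | 2 | 53.8 to 50.3 (7%) | 47.6 to 40.6 (15%) |
| 0.5 | 3 | 53.1 to 47.7 (10%) | 46.3 to 35.4 (23%) |
| 0.3 | 1 | 45.0 to 45.0 (0%) | 30.0 to 30.0 (0%) |
| 0.3 | 1.5 | 44.4 to 42.6 (4%) | 28.7 to 25.2 (12%) |
| 0.3 | 2 | 43.9 to 40.8 (7%) | 27.7 to 21.6 (22%) |
| 0.3 | 3 | 43.1 to 38.3 (11%) | 26.2 to 16.7 (36%) |

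The values of p, HR, bH and bL are assumptions; none is in the documents. The last column is an extreme case, since one group always bleeds and the other never does. Each entry is an average of single-cycle percentages. SAP 5.7.1 also plans cumulative rates per reference period and does not say whether a woman needs one or all three cycles to count, so those figures would differ in size.

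**The case against.** Much of the case on the other side stands.

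- **The link between dropout and bleeding is assumed.** SAP 5.1.1 lists many reasons for leaving, including loss to follow-up, pregnancy, a wish for pregnancy and sponsor request. Bleeding is not a category of its own, and the 45% is not broken down. A ratio of 2 or 3 on dropout for any cause is a strong assumption, and at 1 nothing happens.
- **No improvement claim is planned.** The bleeding endpoints are descriptive, with confidence intervals but no trend test or change-over-time endpoint. A reader might infer that the plan builds in a bias towards LF111. The documents support only that such a bias is possible.
- **The attrition is partly visible.** SAP 4.1 requires the number with data for continuous summaries and a footnote on each percentage denominator. SAP 5.1.1 tabulates withdrawal reasons by cycle and sorts three of them by relation to IMP; SAP 5.6.1 tabulates TEAEs leading to termination. Women who leave are therefore not lost to the report. But none of these outputs is linked to bleeding, so they signal selection without measuring it. The added cycles 2-13 period does not measure it either.
- **The figures add little.** Those showing subjects by cycle or period plot counts of women, which fall under any dropout. That is a separate matter and is not relied on here.

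A reader might also take 45% dropout to mean that the last column holds little more than half of the women in the first. That compares finishers with all starters; the ratio between the two columns is about two-thirds.

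**Conclusion.** The point holds as a limit on interpretation. With available-cycle denominators, a difference between early and late columns mixes change within women with change in who remains, and nothing planned for bleeding separates them. The direction favours LF111 only if women with more bleeding leave more often, which is plausible but not shown by the documents.

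Under 45% dropout, a constant hazard and hazard ratios of 1.5 to 3, the spurious relative fall is about 4-11% with the milder bleeding split and 9-36% with the extreme one. These are illustrations, not estimates. The denominator rule also excludes women still on treatment whose diaries fail the completeness rule, so the contributing group is not simply everyone still taking tablets. The issue is confined to a descriptive tolerability result, and the remedy is a worthwhile low-cost improvement.

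**What to change.** In SAP 5.7.1 keep the planned tables as a description of women with the cycle available. For unscheduled bleeding, unscheduled spotting and unscheduled bleeding/spotting, both subjects and days, add:

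- **(a) A same-women panel:** women with valid cycles in both 2-4 and 11-13, the same women in each column, with within-woman change. Label it as describing women who stayed.
- **(b) A split of the cycles 2-4 result** by whether the woman later reached cycles 11-13 or stopped earlier. This looks directly for a link between early bleeding and later dropout, which is the assumption left open above.

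Add one sentence saying that differences between columns of the available-cycle tables are not by themselves within-woman change and are to be read together with (a) and (b). Panel (a) should not become the sole basis for statements about time, because it describes a more selected group.

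The cost is SAP wording and a few extra tables from diary data already collected. They can be labelled as additional to the protocol, as SAP 2.2.4 already does for other bleeding outputs. The downside for the sponsor is that any improvement over time may look smaller.
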